Recruitment and retention strategies will be adapted iteratively during the study. Prior to enrollment of clinics 2 and 3, we will meet with administration and key healthcare workers from SPH to share our qualitative recruitment results from clinic 1 (Belleville) and brainstorm modifications that hold promise for successful recruitment of healthcare workers and patients at SPH's clinics 2 and 3. Data on recruitment and retention will be obtained through interviews with a subset of healthcare workers (e.g., rural providers, schedulers, and administrators) and patient participants, and through tracking of recruitment and retention efforts.

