8.3 Participant Identification

8.3.1 Clinic Identification

The pilot will take place in three rural clinics: UW Health Family Practice Clinic in Belleville, Sauk Prairie Healthcare Diabetes Clinic, and Sauk Prairie Healthcare Wound Care Clinic.

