8.4 Subject Recruitment

A total of 45 patient participants and up to 30 healthcare workers will be recruited from the 3 rural clinic sites in Wisconsin. Recruitment will be staggered so that Clinic 1 will be active for 24 months with a target patient enrollment of 20; Clinics 2 and 3 will be active for 18 months with a target patient enrollment of 25 total. This translates into a targeted rate of enrollment of 4.5 patients per activated clinic every 6 months. The initial recruitment strategy outlined below will be used to recruit patient participants from the first clinic. Recruitment strategies will be iteratively adapted one month prior to enrollment of the second and third clinics, and again at the end of the pilot. Changes to recruitment will be submitted to the IRB prior to implementation, as needed. Specific recruitment strategies are as follows:

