11.2 Recruitment and Retention Data Collection (Quantitative Data Collection)

We will use recruitment and retention data to assess the impact of the initial strategies and subsequent adaptations. We will keep logs of participant recruitment and retention. For healthcare worker (rural providers and schedulers) recruitment, we will record how many healthcare workers at each site: 1) were emailed an invitation to the recruitment meeting, 2) met with the study PI or research coordinator, and 3) consented to participate. Retention for healthcare workers will be defined as not having withdrawn consent to participate in the study and will not be based on their use of the integrated care model, since deviation from the model will be allowed if it is in the best interest of the patients as determined by the participating rural provider. Retention for administrators and other staff not formally consented in the quantitative portion will be defined as willingness of the clinic to continue to support the research endeavors.

For patient participant recruitment, we will record the number of patients who: 1) were contacted by phone, 2) completed the face-to-face appointment, and 3) consented to participate. For patient participant retention, we will log how many patient participants withdrew from the study or were lost to follow up before the 3-month telephone call. Logs will separate data into three distinct groups corresponding to adaptive iterations of the recruitment and retention strategies.

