11.3.2 Quantitative Data Analysis

[name] will serve as the study's biostatistician and be available to assist with the quantitative data analysis. We will calculate recruitment and retention rates prior to activating the next clinic. We will compare results to our goals of 60% and 80%, respectively.^{34,35} We will create recruitment and retention cascade graphics for both healthcare workers and patients to assist with determining which steps in the process have the highest attrition. Subsequent adaptations will focus on these steps. We will use descriptive statistics, such as counts, rates, and percentages, to summarize recruitment and retention during each cycle of adaptation. The denominator for healthcare worker recruitment steps will be the number of healthcare workers emailed to attend an informational meeting. The denominator for healthcare worker retention will be the number enrolled in the study. Retention will be assessed every 3 months until the end of the study, varying across each clinic due to staggered activation. The denominator for patient recruitment will be the number of patients we attempted to contact by telephone. The denominator for patient retention, assessed at the 3-month follow-up telephone call, will be the number of patient participants enrolled in the study. Comparisons of recruitment and retention between adaptations will be performed using ANOVA or chi-square tests, depending on the outcome types for these endpoints. Also, correlative measures will be calculated when such methods are informative.

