11.4 Cooperative Co-design for Recruitment & Retention Adaptations

Recruitment and retention strategies have been iteratively adapted prior to enrollment of clinics 2 and 3, leading to protocol changes from version 1.4 to 2.0. At the end of the pilot, a co-design meeting will occur with the Cooperative to further refine recruitment and retention strategies with the goal of preparing for a larger, statewide trial using their network of rural healthcare clinics. Our research study team, led by the PI, will present quantitative and qualitative analysis of the most current recruitment and retention strategies (outlined above). Cooperative participants include clinicians, nurses, administrators, and quality improvement experts. We will invite two patient representatives from each activated clinic to participate. Cooperative members include patients in their meetings specifically to ensure patient-centeredness.

During the co-design session, we will use participatory ergonomics, which is a systems engineering approach where the researchers spearheading the study work side-by-side with stakeholders to design it.^{38,39} We used this same approach with the Cooperative to successfully identify health system barriers exacerbating rural disparities in major amputations and design our integrated care model.^{23,24} Research coordinators will distribute adaptations to participating healthcare workers at each activated clinic with explanations for the changes linked to their feedback.

All enrolled patient participants will receive a mailed update after each modification and at the close of the study, detailing our findings and adaptations. These steps are critical not only in keeping participants informed of protocol changes but also in providing evidence of responsiveness to their feedback, which has been linked to study retention.⁴⁰⁻⁴³

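### The planned tests of recruitment between adaptations are confounded with clinic and health system, fully for healthcare workers and fully or partly for patients, so a setting difference could be credited to the adaptation

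*Combined protocol and SAP*

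**What the plan says.** Section 11.2 gives the purpose: "We will use recruitment and retention data to assess the impact of the initial strategies and subsequent adaptations". It defines the groups by adaptation, not by clinic: "Logs will separate data into three distinct groups corresponding to adaptive iterations of the recruitment and retention strategies". Section 11.3.2 then adds significance tests to the descriptive rates: "Comparisons of recruitment and retention between adaptations will be performed using ANOVA or chi-square tests". It gives no alpha, clinic term, within-clinic contrast or caveat about setting.

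The timing of the strategies is in Sections 7.1, 8.4 and 11.4. On the starting point, Section 8.4 says: "The initial recruitment strategy outlined below will be used to recruit patient participants from the first clinic". It says strategies will be "iteratively adapted one month prior to enrollment of the second and third clinics, and again at the end of the pilot". Section 7.1 describes the first of these adaptations as a meeting with Sauk Prairie staff to "brainstorm modifications that hold promise for successful recruitment of healthcare workers and patients at SPH's clinics 2 and 3". Section 11.4 confirms that strategies were "iteratively adapted prior to enrollment of clinics 2 and 3, leading to protocol changes from version 1.4 to 2.0".

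Section 8.3.1 names the clinics: "UW Health Family Practice Clinic in Belleville, Sauk Prairie Healthcare Diabetes Clinic, and Sauk Prairie Healthcare Wound Care Clinic". Section 9.1 adds that the care algorithm is used by primary care providers at Belleville and by diabetes and wound care specialists at Sauk Prairie.

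**The concern.** A test between adaptations answers the question in Section 11.2 only if the groups are otherwise comparable. Here the initial-strategy group is Belleville, and the adapted-strategy group is wholly or mainly Sauk Prairie. The two differ in health system, in provider type and in how patients are found: a weekly data-service list at Belleville, and review of upcoming schedules in the electronic record at Sauk Prairie (Section 8.4.2). Any of these could move the recruitment rate with no help from the adaptation.

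Recruitment and retention strategy is the second primary objective, and the results go to the co-design session that prepares the statewide trial (Section 11.4). A setting difference read as a strategy effect would carry the wrong lesson into that trial.

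**Working it through.** **Layout.** Section 8.4 targets 4.5 patients per active clinic per 6 months. This reproduces: 45 / (24/6 + 2 × 18/6) = 45/10 = 4.5. Belleville is thus alone for months 1–6 and open alongside Sauk Prairie for months 7–24. The second adaptation point is the end of the pilot, with no enrollment after it, so only one recruitment adaptation can be compared.

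**What can be estimated.** Write each clinic-period as (intercept, adaptation, health system).

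- Belleville keeps the initial strategy throughout: rows (1,0,0) for Belleville and (1,1,1) for Sauk Prairie. The rank is 2 for 3 parameters. Adaptation and system are the same column, and adding clinic to the model leaves no adaptation effect to estimate.
- Belleville switches when Sauk Prairie opens: rows (1,0,0), (1,1,0) and (1,1,1). The rank is 3. A within-Belleville contrast exists, but Section 11.3.2 does not use it.

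Healthcare workers are recruited about one month before each clinic's activation (Section 8.4.1), so the first case applies to them. Belleville also recruited 100% of them (Section 7.1), so that comparison cannot show an improvement.

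**Size for patients.** The documents do not give the number of patients contacted. Assumptions:

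- alpha 0.05, two-sided Pearson chi-square without continuity correction;
- contacts = 27 enrolled (Section 13.2) / 0.60 goal rate = 45;
- contacts split 20 Belleville and 25 Sauk Prairie, in the ratio of the Section 8.4 enrollment targets;
- no true adaptation effect, only a setting difference.

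If Belleville switched at month 6, its contacts split as 20 × 6/24 = 5 before and 15 after. The groups become 5 versus 15 + 25 = 40. The expected false difference is then diluted: at 40% versus 70%, (15 × 0.40 + 25 × 0.70)/40 − 0.40 = 0.1875, about 19 points instead of 30. At 40% versus 60% it is (15 × 0.40 + 25 × 0.60)/40 − 0.40 = 0.125.

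Exact enumeration of the test gives the chance of a significant adaptation result:

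| Belleville vs Sauk Prairie rate | Never switched (20 vs 25) | Switched at month 6 (5 vs 40) |
|---|---|---|
| 60% vs 60% | 4.9% | 4.4% |
| 40% vs 60% | 26.2% | 7.7% |
| 40% vs 70% | 52.3% | 11.8% |

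**Sensitivity to the number of contacts.** Had the target of 45 been enrolled at 60%, contacts would be 20/0.60 ≈ 33 and 25/0.60 ≈ 42. At 40% versus 70% the figures are then 76% (33 vs 42) and 17% (8 vs 67, with 5/0.60 ≈ 8 contacts before the switch and 25 + 42 = 67 after).

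**What a within-Belleville contrast could show.** With 8 contacts before and 15/0.60 = 25 after, power is about 0.40 even for a change from 35% to 69%, the precedent cited in Section 5.4.2. Such a contrast can only be descriptive.

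**Retention.** The one revision that Section 8.5.1 marks as new is the patient letter, mailed to all enrolled patients. Its before/after comparison is confounded with calendar time, not with clinic.

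**The case against.** The strongest reply is that no decision hangs on this p-value. Section 13.1 lists no recruitment hypothesis. The endpoint is meeting 60% and 80%. Section 11.3.2 relies mainly on rates and attrition cascades, and final strategies come from co-design using qualitative results as well. That is right, and it limits the damage: the test is one input, not a rule for choosing strategies. It does not make the test valid for the purpose in Section 11.2.

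A second reply is that clinic is already handled: healthcare-worker logs are kept by site (Section 11.2), and Section 13.2 stratifies primary outcomes by clinic. But Section 13.2 describes the care-process and amputation models, and stratification cannot separate strategy from clinic where the two coincide.

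A third reply is that Belleville stayed open alongside Sauk Prairie for 18 months, and Section 11.4 has adaptations distributed to healthcare workers at each activated clinic, so the confounding may be only partial. This stands for patients. The documents leave it open, and the error rates depend heavily on the answer.

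A reader might also infer that every adaptation is tied to its own clinic and system, and that retention is affected in the same way. The documents do not support that. One recruitment adaptation precedes enrollment, it coincides with two clinics in one system, and the retention letter is not aligned with clinic.

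**Conclusion.** The concern holds in a limited form. As written, Section 11.3.2 can report a Belleville versus Sauk Prairie difference as an adaptation effect. The confounding is complete for healthcare-worker recruitment. For patient recruitment it is complete if Belleville kept the initial strategy and partial if it switched.

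A reader might take 52% as the error rate of the planned test. It is the larger of two scenarios for one assumed setting difference, and it requires that Belleville never switched. Across the two setting differences and both scenarios, at 45 contacts, the range is about 8% to 52%. The contact total assumes that the 60% goal was met, although Sections 7.1 and 16.3 say patient recruitment fell short of expectations. The 40% versus 60% case implies 20 × 0.40 + 25 × 0.60 = 23 enrolled, not 27. The figures show the order of magnitude and are not estimates for this trial. The confounding itself does not depend on them.

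**What to change.** In Section 11.3.2:

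- Replace the pooled between-adaptation tests of recruitment with recruitment rates by clinic and adaptation period, with exact 95% confidence intervals. Report retention the same way.
- State whether and when Belleville adopted the version 2.0 recruitment changes. If it did, show its before and after rates descriptively. If it did not, say that no within-clinic recruitment contrast exists.
- State that differences between Belleville and Sauk Prairie are not attributed to the adaptations, and that the comparison before and after the patient letter is confounded with calendar time.

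The cost is a wording change and a different tabulation of the same logs. With 27 patients over three clinics the cells will be small and the intervals wide, and there will be no headline p-value.

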11.4 Cooperative Co-design for Recruitment & Retention Adaptations

Recruitment and retention strategies have been iteratively adapted prior to enrollment of clinics 2 and 3, leading to protocol changes from version 1.4 to 2.0. At the end of the pilot, a co-design meeting will occur with the Cooperative to further refine recruitment and retention strategies with the goal of preparing for a larger, statewide trial using their network of rural healthcare clinics. Our research study team, led by the PI, will present quantitative and qualitative analysis of the most current recruitment and retention strategies (outlined above). Cooperative participants include clinicians, nurses, administrators, and quality improvement experts. We will invite two patient representatives from each activated clinic to participate. Cooperative members include patients in their meetings specifically to ensure patient-centeredness.

During the co-design session, we will use participatory ergonomics, which is a systems engineering approach where the researchers spearheading the study work side-by-side with stakeholders to design it.^{38,39} We used this same approach with the Cooperative to successfully identify health system barriers exacerbating rural disparities in major amputations and design our integrated care model.^{23,24} Research coordinators will distribute adaptations to participating healthcare workers at each activated clinic with explanations for the changes linked to their feedback.

All enrolled patient participants will receive a mailed update after each modification and at the close of the study, detailing our findings and adaptations. These steps are critical not only in keeping participants informed of protocol changes but also in providing evidence of responsiveness to their feedback, which has been linked to study retention.⁴⁰⁻⁴³

12.0 DATA HANDLING AND RECORD KEEPING

12.1 Data Collection

12.1.1 Data Collection

Standardized data collection forms (e.g., source documents, case report forms, standardized assessment forms, etc.) are used to ensure data collected are consistent and compliant with the protocol and IRB application.

Data collection is the responsibility of the research coordinators under the supervision of the Principal Investigator (PI). The PI is responsible for ensuring the accuracy, completeness, legibility, and timeliness of the recorded and reported data.

All data collection forms must be completed in a legible manner; any missing data will be explained. Data entry errors will be corrected with a single line through the incorrect entry and the correct data is entered above/near the correction. All changes will be initialed and dated. Forms will be filled out electronically or using black or blue ink.

Data collection forms are maintained in the subject files and retained as described in Section 12.3: Records Retention.

Data collection will be done through manual chart abstraction by [name], [name], and/or [name]. These individuals will be granted remote access to all three clinics' electronic medical record. A business associate agreement (BAA) with SPH will be put in place for this purpose. A unique study ID will be assigned to each patient participant. A key linking the patient participant's ID and the study ID will be kept on the HIPAA compliant HIP server and UW Restricted ResearchDrive. A coded dataset will be created on the HIP servers/UW Restricted ResearchDrive and REDCap for analytic purposes and ICTR DMC oversight purposes.

Study data will be documented and monitored in SMPH REDCap. Data will be collected on paper as described above, recorded by either the study participant or research staff, then electronically entered, with confirmation of correct entry, by the research staff via REDCap on research computers. To gain access to the REDCap system, study team members will need to fill out a REDCap account request through ICTR and complete required training using the following link:

<https://redcap.ictr.wisc.edu/surveys/?s=DWJFCLFHYL8PKJRT>

Once approved, each user will have their own account. To ensure that REDCap users have access only to data and information that they are supposed to have access to within the application, each user's privileges will be assigned by the study's principal investigator or the study team member that created and manages the REDCap project database. After REDCap entry, source documents will be stored in a locked filing cabinet in [name] office location within the secure UW Medical Foundation Centennial Building, and maintained for the length of time approved by the IRB.

12.1.2 Data Management

All electronic data will be stored on the Health Innovation Program's servers and the PI's/[name]'s UW Restricted ResearchDrive and/or entered into the SMPH REDCap database. The study team will have access to these application servers for statistical processing; data storage for datasets with personal health information (PHI); backup and recovery; technical, physical, and management security and privacy controls; ongoing review of regulatory agreements and access compliance; remote access to IT resources; and IT helpdesk support. The data will be stored in a location on the servers that will be restricted to approved members of the study team. Additionally, the REDCap database will be used by the ICTR DMC, which is providing oversight for this clinical trial. Printed and signed consent forms and other printed study materials will be kept in a locked cabinet in [name] office location within the secure UW Medical Foundation Centennial Building.

Additionally, a spreadsheet of coded data collected from all study participants will be loaded to a UW Box folder for the statistician to access for data analysis.

12.2 Confidentiality and Privacy

Research participant confidentiality and privacy are strictly held in trust by the participating investigators, their study team, and the sponsor and their agents. Therefore, the study protocol, documentation, data, and all other information generated will be held in strict confidence. No information concerning the study or the data will be released to any unauthorized third party without prior written approval of the sponsor.

All research activities will be conducted in as private a setting as possible. Audio recordings of interviews will be obtained using a recording device that is kept in the possession of the research coordinator when in use and in locked rooms limited to essential personnel when not in use. Transcription will be conducted by members of the study team (HIP student hourlies with appropriate IRB and HIPAA training add to the research team roster for this specific purpose, [name] and/or [name]) and individual identifiers will be redacted prior to sharing this information as part of interviews and co-design meetings.

All study team members engaged in the conduct of this project have completed training on the protection of human subjects and the Health Insurance Portability and Accountability (HIPAA) Privacy Rule. In addition, all key personnel (i.e., Principal Investigator, individuals involved in identifying/recruiting subjects, obtaining informed consent, or interacting and intervening with research study participants) have undergone both Human Subjects and Good Clinical Practice (GCP) training.

Information about study participants will be kept confidential and managed according to HIPAA requirements. All study participants will provide informed consent, with prospective patient participants receiving the integrated care intervention also providing consent on a combined consent and HIPAA

authorization form that includes specific privacy and confidentiality rights. Study data will be maintained per federal, state, and institutional data policies.

The investigator(s) will ensure that the identities of study participants are protected by using coded information specific to each participant. The log of participant-identifying information that links participants to their study-specific identification number will be maintained by the investigator and research study team. Hard copy logs and all study records will be maintained in locked rooms and access will be limited to essential study personnel. Electronic study records/files will be stored on HIPAA-compliant Health Innovation Program servers and [name]'s Restricted ResearchDrive and accessed via networked computers that are password-protected with access provided only to authorized study personnel.

Authorized representatives of the following groups may need to review this research as part of their responsibilities to protect research subjects: authorized representatives of the sponsor, representatives of the IRB, DSMB/DMC, regulatory agencies, and federal oversight agencies. The clinical study site will permit access to such records.

Research coordinators may use e-mail to communicate with research participants, if the participant has agreed to using email in the Informed Consent form. The information contained in emails will be limited to study visit time and date information, general questions, etc. All emails to participants will be sent from UW/wisc.edu accounts; personal, home, or Gmail email accounts will not be used.

